14.2. INSTITUTIONAL REVIEW BOARD (IRB) / ETHICS COMMITTEE (EC) INFORMATION

15. CLINICAL CENTERS

16. DATA HANDLING

17. DATA ANALYSIS

## PROTOCOL SUMMARY

Title:	Advanced Model Based Fast Anatomical Mapping Software for Atrial Fibrillation Ablation (mFAM-2)
Objective:	This prospective, multicenter observational study will examine: 1) The accuracy of left atrial anatomy reconstruction using updated mFAM software 2) The left atrial geometry creation time 3) Fluoroscopy time for left atrial anatomy creation
Design:	This is a prospective, multi-center, non-randomized observational trial. The total enrollment will be up to 150 patients.
Enrollment:	
Eligible subjects will be consented for participation in the trial prior to undergoing first-time ablation for atrial fibrillation. Patients are considered eligible if they meet the following criteria:
 
 
1. Age <math>\geq</math> 18 years
 
2. Have either paroxysmal, persistent, or longstanding persistent AF, which are defined as follows: 
 
1) Paroxysmal AF – episodes of AF lasting <math><</math> 7 days and terminate without electrical or pharmacologic cardioversion
 
2) Persistent AF – episodes of sustained AF <math>></math> 7 days, or episodes of AF which are terminated by electrical or pharmacologic cardioversion after <math>\geq</math> 48 hours.
 
3) Longstanding persistent AF – episodes of AF lasting longer than one year.
 
 
 
3. Are planned to undergo a first catheter ablation procedure for AF (prior ablation for typical atrial flutter or supraventricular tachycardia is allowed)
 
4. Have the ability to understand the requirements of the study and sign the informed consent form.
 
5. Are willing to adhere to study restrictions and comply with all post-procedural follow-up requirements
 
 
Patients will be excluded from the trial if they have:
 
 
1. Rheumatic heart disease,
 
2. Current intra-cardiac thrombus,
 
3. Class IV HF,
 
4. Unable to sign consent
 
5. Unstable angina
 
6. Recent cerebral ischemic events
 
7. Contradiction to anticoagulation
 
8. Recent cardiac surgery (CABG or valve replacement within 6 months)
 
9. Complex congenital heart disease
 
 
Patients are considered enrolled once consented. Patients who do not undergo AF ablation within 90 days of enrollment will be considered to be screen failures.
 
Up to 150 subjects are expected to be enrolled in the study.

Clinical Sites:	1. Mount Sinai Hospital, New York, NY 2. Grandview Medical Center, Birmingham, AL 3. Naples Community Hospital, Naples, FL 4. Cleveland Clinic, Cleveland, OH
Time Course:	Expected duration of patient enrollment is approximately 6 months to 1 year.
Subject Description:	Subjects will only be eligible for this study if they are $\geq$ 18 years of age, have a history of AF, and are planned for AF ablation
Endpoints:	1. Accuracy of map (defined as the distance between the acquired points and the surface of the left atrial geometry) 2. Left atrial geometry creation time 3. Total Fluoroscopy time (for sites that use fluoroscopy)
Follow-Up	Until hospital discharge
Study Sponser:	[name] , M.D. Icahn School of Medicine at Mount Sinai [name]
Site, Monitoring, and Data Management Center	Electrophysiology Clinical Research Group Icahn School of Medicine at Mount Sinai [name]

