## 2 STUDY OBJECTIVE

This prospective, multicenter observational study will examine the ability of model based fast anatomical mapping (mFAM) with additional software modifications to create left atrial (LA) geometry and guide atrial fibrillation ablation.

Specifically, the study will assess the following issues in atrial fibrillation ablation:

- 1) The accuracy of left atrial anatomy reconstruction, defined as the distance between the acquired points and the surface of the left atrial geometry.
- 2) Left atrial geometry creation time
- 3) Fluoroscopy time for left atrial anatomy creation, for those sites which use fluoroscopy

[figure not shown]
We hypothesize that this approach will lead to accurate LA geometry creation for AF ablation more rapidly than standard techniques without a significant increase in fluoroscopy time.

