## 6 ENDPOINTS

### PRIMARY CLINICAL ENDPOINTS

1. Accuracy of map (defined as the distance between the ablation points and the surface of the mFAM geometry)
2. Left atrial geometry creation time
3. Fluoroscopy time

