### 10.3 PROCEDURAL DETAILS

- Patients will be brought to the electrophysiology laboratory in a fasting state
  - Patients will have transseptal access with administration of anticoagulation to achieve activated clotting time of at least 300 seconds at the time of the initial left atrial ablation lesions. If esophageal deviation is planned, it will be performed prior to creation of left atrial geometry and ablation of the target vein pair.
- The CARTO3 mapping system and mFAM software will be used to create left atrial geometry and ablation will be performed to isolate pulmonary veins as per standard practice.
  - If esophageal deviation was performed, after completion of one PV vein pair the esophagus will be deviated again and a new left atrial map will be created (if needed).
  - Adjunctive assessment of anatomy and ablation sites with real-time electrogram monitoring, intracardiac echocardiography (ICE), and fluoroscopy will be performed as per standard.

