- Pseudoaneurysm: development of a false pouch in the vessel wall. This can be caused by movement of catheters in the blood vessels. This may heal on its own, but sometimes need surgical repair (<1%).
- Radiation injury resulting in dermatitis (skin burns): (<1%).
- Respiratory failure: damage to breathing that can be permanent (respiratory arrest) (<1%).
- Radiation exposure during the fluoroscopic imaging of the catheters during ablation: this may slightly increase the lifetime risk of developing a fatal malignancy or a genetic defect in offspring (<1%).
- Fluid overload: excessive fluid built up could result in pulmonary (lung) edema; congestive heart failure (CHF) may occur or may be exacerbated (worsened) due to delivery of sterile salt water (saline) during the procedure (these risks are specific to open irrigated ablation catheters) (1.5%).

The protocol requires a CT or MRI scan be performed. Routine CT or MRI scanning with contrast is often performed if there are no contraindications as part of normal pre-procedural planning. If the patient has impaired renal functions or has abnormal renal function, CT/MR imaging will be deferred.

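### The fluoroscopy endpoint is inconsistent in scope: objective 3 concerns building the left atrial anatomy, the Summary endpoint is a total, and Section 6 states no scope

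*Combined protocol and SAP*

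**What the plan says.** Five statements in the combined protocol and SAP bear on the scope of this measure.

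- Protocol Summary, Objective, item 3: "Fluoroscopy time for left atrial anatomy creation".
- Section 2, item 3: "Fluoroscopy time for left atrial anatomy creation, for those sites which use fluoroscopy".
- Protocol Summary, Endpoints, item 3: "Total Fluoroscopy time (for sites that use fluoroscopy".
- Section 6, primary clinical endpoints, item 3: "Fluoroscopy time", with nothing further.
- Section 2, hypothesis: accurate geometry "more rapidly than standard techniques without a significant increase in fluoroscopy time", again without saying which part of the procedure is meant.

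Section 10.3 describes how fluoroscopy is used: "Adjunctive assessment of anatomy and ablation sites with real-time electrogram monitoring, intracardiac echocardiography (ICE), and fluoroscopy will be performed as per standard". For cases with esophageal deviation it also provides that "a new left atrial map will be created (if needed".

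**The concern.** Fluoroscopy time is one of three primary endpoints. The objective limits it to one phase of the procedure. The Summary endpoint, read plainly, does not.

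Sections 8 and 17 describe a feasibility study analyzed by means and standard deviations. The reported mean is therefore the whole result for this endpoint, and a reader has to know what was timed. A whole-procedure mean would be reported against an objective about mapping, and would mix in fluoroscopy that has nothing to do with how the geometry was made. If only a total were recorded, the mapping part might not be recoverable afterwards.

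**Working it through.** No fluoroscopy figure appears in the plan, so there is nothing to reproduce. The check is a comparison of the text.

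**Step 1: scope and site limit, statement by statement.**

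| Place | Scope | Limited to sites using fluoroscopy? |
|---|---|---|
| Protocol Summary, Objective | Anatomy creation | Not stated |
| Section 2, objective | Anatomy creation | Yes |
| Protocol Summary, Endpoints | Total | Yes |
| Section 6, primary endpoints | Not stated | Not stated |
| Section 2, hypothesis | Not stated | Not stated |

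Of the four objective and endpoint statements, two say anatomy creation, one says total and one is silent. The site limit is present in two and absent from two. That absence is an omission and not a second conflict.

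**Step 2: does anything else settle the scope?** No. Table 1 in Section 5 has no row for fluoroscopy. Section 10.3 gives no start or stop for timing it and no rule for adding up repeat maps. Section 17 does not define the variable.

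**Step 3: are the two quantities different under this protocol?** Let A be fluoroscopy time during anatomy creation and R the fluoroscopy time in the rest of the procedure. The procedure total is T = A + R, and T equals A only if R = 0. Section 10.3 names ablation sites alongside anatomy as things assessed with fluoroscopy, so R is not zero by design. The generic risk list in Section 12 points the same way: "Radiation exposure during the fluoroscopic imaging of the catheters during ablation".

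**Step 4: how large is the gap?** If A is a share f of T, then T / A = 1 / f. The documents give no A, R, T or f. The ratio could lie anywhere from 1 (when R = 0) upward. Any single value would be an assumption, so none is offered as evidence.

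**Step 5: what does the missing site limit do?** Suppose n1 patients are treated at sites that use fluoroscopy and n0 at sites that do not. Entering the latter as zeros multiplies the mean by n1 / (n1 + n0). Neither number is given, so this effect cannot be sized either.

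**The case against.** **Total need not mean the whole procedure.** Section 10.3 allows a second map, so the word could mean a sum over maps. On that reading there is no conflict. This stands as a possibility, and it is why the point is an inconsistency in scope and not a proven contradiction. But the text does not say so, and whole procedure is the plainer meaning.

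**The total may be what the sponsor wants.** Section 2 states the aim as making the geometry and also guiding ablation, and Section 3 says the software changes are meant to help both mapping and ablation. A procedure total fits that wider aim. This stands: the documents do not settle which scope is right, so the sponsor must be free to change the objective instead of the endpoint.

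**Anatomy creation has no clean end.** Section 3, including its Figure 2, has the model adapting to ablation points, so the geometry can still be changing during ablation. This also stands. A window that closes when the geometry is accepted would rest on a step the protocol does not contain.

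**The consequence is small.** There is no threshold, comparator value or test for fluoroscopy. This is correct, and it limits the weight of the point without removing the mismatch.

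A reader might also infer that sites will record different quantities, or that the case report form captures the wrong one. The documents support neither. Section 13.4 has the coordinating center issue the forms, which argues for a common field, and the form itself is not shown.

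**Conclusion.** The point holds as an inconsistency in the scope of one primary endpoint. If the Summary endpoint is followed as it most plainly reads, it does not measure objective 3. The conclusion rests on that plain reading of total and on Section 10.3 using fluoroscopy for ablation sites as well as anatomy.

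The effect is confined to one descriptive result, and its size cannot be computed from the documents. It would be wrong to infer lost power or an error-rate problem, since Section 8 says the sample size was not set statistically and Section 17 plans no test. It would be equally wrong to think that settling the scope makes the hypothesis in Section 2 testable: the comparison with standard techniques would still have no control group. The point is worth correcting because the correction is cheap and may not be possible once only totals have been recorded.

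**What to change.** 1. Record and report two quantities for each case: (a) fluoroscopy time during left atrial anatomy creation, summed over repeat maps; (b) total procedural fluoroscopy time.
2. Name (a) as the endpoint that answers objective 3. If the sponsor intends the total, reword the objective to match. Either way, use one wording in the Protocol Summary (Objective and Endpoints), Section 2 and Section 6.
3. The sponsor should set the start and stop of the anatomy window, stating how it treats model adaptation during ablation and SoundFAM ultrasound acquisition (both Section 3), and cases that revert to the non-study software (Section 11).
4. Carry the limit to sites that use fluoroscopy into the Summary objective and Section 6, so that sites using none do not enter the mean as zeros. At a site that does use it, count a case without fluoroscopy as 0 minutes.

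The cost is wording in four places and, if the case report form does not already capture them, a few clock readings. With one start and one stop per map plus a procedure total, that is 2 × 1 + 1 = 3 readings per case, or 2 × 2 + 1 = 5 with a second map. For 150 patients, with every site using fluoroscopy, this is 3 × 150 = 450 readings with one map each and 5 × 150 = 750 with two. A window that reopens during ablation would need more.

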## 2 STUDY OBJECTIVE

This prospective, multicenter observational study will examine the ability of model based fast anatomical mapping (mFAM) with additional software modifications to create left atrial (LA) geometry and guide atrial fibrillation ablation.

Specifically, the study will assess the following issues in atrial fibrillation ablation:

- 1) The accuracy of left atrial anatomy reconstruction, defined as the distance between the acquired points and the surface of the left atrial geometry.
- 2) Left atrial geometry creation time
- 3) Fluoroscopy time for left atrial anatomy creation, for those sites which use fluoroscopy

[figure not shown]
We hypothesize that this approach will lead to accurate LA geometry creation for AF ablation more rapidly than standard techniques without a significant increase in fluoroscopy time.

## 3 INTRODUCTION, RATIONALE AND BACKGROUND

Atrial fibrillation (AF) ablation for paroxysmal and persistent atrial fibrillation typically involves pulmonary vein isolation (PVI) with left atrial endocardial ablation. With a radiofrequency (RF) ablation approach, the left atrial geometry can be defined using electroanatomical mapping systems.

Reconstruction of left atrial geometry using the CARTO3 system (Biosense Webster, Diamond Bar, CA) is currently performed using a multielectrode mapping catheter that is localized in 3D space utilizing magnetic- and impedance-based technologies with a functionality called FAM (fast anatomical mapping). An alternative approach to creation of left atrial geometry using a novel technique based on a library of previously defined left atrial archetypes – called “mFAM” – has been studied in this investigator-initiated FDA IDE protocol..

[figure not shown]
mFAM applies a model based approach for reconstruction of left atrial chamber anatomy. The model created by fitting a parametric shape model to the point cloud acquired by a catheter. The model includes a geometrical primitive for each of the pulmonary veins, the left atrial appendage, the left atrial chamber, and the mitral valve (as seen in Figure 1-A). The geometrical primitives are blended to form the left atrial structure (as seen Figure 1-B).

*Figure 1: A: Model components. B: Blended model, superimposed on all catheter points' samples (blue), and locations where the catheter was in contact with the surface (yellow).*

A set of more than 200 atrial CT scans were used to initially develop and train this model and define relevant proportions and sizes for “realistic” and anatomically accurate left atria. Examples of these features are: the angle between the PVs, distances from atria center to the mitral valve and pulmonary vein ostia, and the ratio of these values to left atrial volume. This approach provides a way to represent the most probable left atrial geometry with limited information.

This anatomy could be adapted to more accurately represent clinically important points. For points of importance, such as ablation sites, the model deforms to align with the location when there is contact while keeping proportion and sizes congruent with the existing defined anatomical information (as seen in Figure 2).

*Figure 2: A: Model with original catheter points (gray dots), left side ablation points (blue spheres), first right side ablation point (yellow sphere). B: Adaptation of the model to first right side ablation point. C: Final model, adapted to right side ablation points.*

This model-based fast anatomical mapping strategy has proven feasible in retrospective analyses, and the anatomy has been validated in a pilot study of 21 patients with anatomy in the left atrium collected with a force-sensing catheter. Distance between the mFAM generated anatomy and the reference anatomy was further improved when Navistar data was added to it (see Figure 3). In the current trial, mFAM has been used prospectively to reconstruct left atrial geometry reconstruction for AF ablation procedures..

[figure not shown]

Figure 3: Validation results on a pilot study of 21 patients using a Lasso/Pentaray alone or with Navistar data with 5-10 grams of force. With addition of the Navistar data, distance to reconstruction < 2mm.

In this protocol amendment, we propose expanding enrollment in this multi-center, non-randomized study to evaluate additional improvements on this software solution to guide AF ablation.

### Overview of mFAM and Software Improvements

The mFAM Workstation is a computerized system used to reconstruct the shape of the left atrium of the heart by fitting a parametric shape model to points data which is obtained by conventional electrophysiological methods acquired by a catheter. The mFAM Workstation uses recorded catheter positions and other data inputs collected using conventional multi-electrode catheters and, using proprietary software algorithms, it generates output data files that are displayed as a 3D anatomic structure.

mFAM improves on the FAM functionality by applying a model-based approach for reconstruction of left atrial chamber anatomy. This approach was tested in the patients initially enrolled in this trial for reconstruction of the left atrial geometry for AF ablation. Since that time, additional software modifications have been made to help to improve accuracy and efficiency of left atrial mapping and ablation during AF ablation procedures. Specifically, the following software enhancements/algorithms have been added:

1. Mechanical Tissue Proximity Indication (mTPI): allows for automatic acquisition of points from a standard multi-electrode catheter. The system uses mechanical deformation properties of the catheter to determine tissue contact.
2. Enhanced Catheter Stability: allows for estimation of catheter stability throughout the respiratory cycle instead of only end-expiration by accounting for real-time respiratory motion during measurement of catheter location.

3. Improvements to the proprietary mFAM algorithm, which applies a model-based approach to reconstruct left atrial geometry.
4. SoundFAM: incorporates ultrasound frames captured with a standard intracardiac ultrasound catheter (Soundstar, Biosense Webster, Diamond Bar, CA) into the model-based reconstruction of left atrial geometry. This feature also allows for 3D reconstruction of the location of the esophagus to determine its relationship to the left atrium, which is critical for AF ablation procedures.

The available results from clinical use in the current IDE trial and from cases done in the EU are listed in Figure 4. Over 98% of all points and 100% of magnet points were located less than 3mm from the recreated left atrial surface.

Data set	Contact Points				Magnets				Number of valid time points	Number of valid cases		
	Mean Distance		RMS Distance		Mean Distance		RMS Distance					
	Mean	% <3mm	Mean value	% <4mm	Mean value	% <3mm	Mean value	% <4mm				
All Cases	1.54	98.4% (370/376)	2.54	93.09% (350/376)	0.89	100% (376/376)	1.23	100% (376/376)	376	119		
IDE	1.5	98.66% (147/149)	2.56	91.28% (136/149)	0.8	100% (149/149)	1.1	100% (149/149)	149	50		

*Figure 4: Data from all cases performed with mFAM software and the cases performed thus far in the current IDE trial*

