## 4. DEVICES, SOFTWARE AND PROCEDURES

### 4.1 MFAM Workstation

The mFAM Workstation operates in direct interface with the CARTO® 3 System V7 workstation. Coordination between the Workstation and the CARTO® 3 System includes:

- Automatic import of data recordings (such as position, respiration, and force) from the CARTO® 3 System
- Analysis of data by proprietary software algorithms
- Transfer of the 3D anatomical structure to the CARTO® 3 System
- Display of the 3D anatomical structure on the monitor of the CARTO® 3 System
- The maps can be superimposed over original 3D maps and the real-time position of the mapping catheter in the CARTO® 3 System.

[figure not shown]

Figure 5: Real time data is acquired by placing the catheter into pulmonary veins and is transferred to the mFAM workstation, where it is processed, and the image maps are transferred back to the CARTO workstation.

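### Accuracy has two definitions; under the acquired-points one, the new contact feature can select the points that both build and score the surface, so a systematic contact error may be partly or wholly hidden

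*Combined protocol and SAP*

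**What the plan says.** The first endpoint has two definitions. The Protocol Summary gives "Accuracy of map (defined as the distance between the acquired points and the surface of the left atrial geometry", and Section 2 agrees: "defined as the distance between the acquired points and the surface of the left atrial geometry". Section 6, which lists the primary endpoints, gives "Accuracy of map (defined as the distance between the ablation points and the surface of the mFAM geometry".

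Section 3 says that the left atrial surface comes from fitting a parametric shape model to the catheter's point cloud. It adds that the model then deforms to ablation sites where there is contact, while keeping anatomical proportions.

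The software overview in Section 3 lists four enhancements. Two bear on this point:

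- **mTPI** "allows for automatic acquisition of points from a standard multi-electrode catheter", and "The system uses mechanical deformation properties of the catheter to determine tissue contact".
- **Enhanced Catheter Stability** estimates stability across the respiratory cycle by "accounting for real-time respiratory motion during measurement of catheter location".

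For the earlier pilot, Section 3 says that the anatomy was "validated in a pilot study of 21 patients with anatomy in the left atrium collected with a force-sensing catheter". The current endpoint names no separate reference. Section 17 plans means with standard deviations and percentages. It plans no check of contact calls.

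**The concern.** A validation endpoint should get worse when the thing it validates fails. If the software under test decides which catheter positions are wall contact, builds the surface from them, and is then scored on the distance from those positions to that surface, a consistent misjudgement of contact moves both sides of the comparison. The reported distance would then measure how well the model fits its own input rather than how close the surface lies to the wall.

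At stake is the first listed endpoint, for one of the four new features and possibly a second. A reassuring millimetre figure could be reported while the surface sits inside the true wall over a region. Because the two definitions use different points, the plan also does not settle which figure will be reported.

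**Working it through.** **Which points, and are they independent of the surface?**

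| | Acquired points (Summary, Section 2) | Ablation points (Section 6) |
|---|---|---|
| Catheter | Multi-electrode mapping catheter for the mTPI points | Ablation catheters listed in Section 4.2 |
| Can mTPI select them? | Yes, per the software overview | Not stated; mTPI is described only for the multi-electrode catheter |
| Do they shape the surface? | Yes, it is fitted to them | Yes, it adapts to them on contact |
| Independent score? | No | Only if scored before that adaptation |

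**Earlier figures.** Figure 4 reproduces: 370/376 = 98.40%, 350/376 = 93.09%, 147/149 = 98.66%, 136/149 = 91.28%. The average mean contact-point distance is 1.54 mm and the RMS 2.54 mm. The surface therefore does not simply pass through its points.

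**How much can be hidden: whole chamber.** All settings are assumptions; the documents give none. The simulation used a sphere of radius 25 mm, 300 points, radial scatter SD 1.5 mm, a least-squares fit of centre *c* and radius *r*, and 100 replicates.

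- Reported distance: mean of | |P − c| − r | over the fitted points P.
- True error: the same expression over points on the true wall.
- Independent score: the same expression over 100 new points with true contact and the same scatter.

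| Scenario (mm) | Reported | True error | Independent score |
|---|---|---|---|
| No error | 1.18 | 0.14 | 1.20 |
| All points shifted 4 in one direction, free fit | 1.19 | 2.01 | 2.27 |
| All points 4 short of the wall, free fit | 1.19 | 4.01 | 4.00 |
| Same, radius pulled towards its true value | 2.11 | 1.98 | 2.12 |
| 30% of points 4 short, free fit | 1.92 | 1.22 | 1.60 |
| Random respiratory error, amplitude 4 | 1.75 | 0.23 | 1.22 |

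Hand checks: with no error, 1.5 × √(2/π) = 1.20. With all points 4 mm short, the fitted radius is 25 − 4 = 21, so the error is 4. For the shift, the mean of |4 cos θ| over a sphere is 4/2 = 2. With 30% short, 0.3 × 4 = 1.2.

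**How much can be hidden: one region.** Again assumed: a circular wall, 25% of it affected, 4,000 points, a flexible 40-bin local fit, scatter SD 1.88 mm. With no false contact the reported mean is 1.49 mm.

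| False contact in the region | Reported mean | On held-out points | True regional error |
|---|---|---|---|
| All points, 2 mm / 4 mm short | 1.49 / 1.49 | 1.51 / 1.51 | 2.01 / 3.99 |
| Half the points, 2 mm / 4 mm short | 1.54 / 1.69 | 1.57 / 1.72 | 1.01 / 1.98 |

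Holding out points that mTPI selected barely changes the score, because they carry the same error. Independent true-contact points do reveal it. With all points false, their mean distance in the region rises from 1.50 mm to 2.29 / 4.00 mm.

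**The case against.** The strongest reply is that Section 6 is the primary endpoint section and scores ablation points, which nothing in the protocol says mTPI selects. That stands. A reader might infer that mTPI chooses the points of the primary endpoint whichever definition applies; the documents do not support that. What remains under Section 6 is the adaptation of the model to ablation sites.

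The second reply is that the fit is not free. The model was developed on more than 200 CT scans and keeps anatomical proportions, and SoundFAM adds ultrasound frames that mTPI does not select. This also stands in part. A reader might infer that errors of the new features always cancel out of the endpoint. The simulation shows near-complete hiding only for systematic error under a flexible fit. A size constraint, scattered false contact and random respiratory error all raise the reported distance. The strength of the real constraint is not given, so the degree of hiding is unknown.

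Third, the respiratory feature is described mainly as a stability estimate. That it sets the stored coordinates of scored points is a reasonable inference, not a statement in the protocol.

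Finally, Section 8 describes a feasibility study sized without statistical means, and the analysis is descriptive with no accuracy threshold. This limits the consequence but supplies no independent reference.

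**Conclusion.** The point holds in a limited form. The two endpoint definitions conflict. Under the acquired-points definition, systematic false-contact error, and possibly respiratory location error, can be shared by points and surface and so be partly or wholly hidden. Under the ablation-points definition, the score is not independent unless it is taken before the model adapts to those points.

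For size: a consistent 4 mm contact error changed the reported distance by between 0.01 mm (1.19 − 1.18, free fit) and 0.93 mm (2.11 − 1.18, with the size constraint). The true errors were 4.01 and 1.98 mm. These figures rest on assumed geometry, scatter and fit; they show the mechanism and do not predict this software's performance.

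Two further inferences should be avoided. The 5-10 g in the Figure 3 caption describes Navistar data added to the reconstruction; it is not stated as the force window of the pilot's reference anatomy. And Figure 4 cannot be taken as wholly preceding the new features: 119 − 50 = 69 cases lie outside the IDE row, and their software version is not given.

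The change is worth making because it is inexpensive and concerns the first endpoint. In a descriptive feasibility study it is an improvement, not a fatal flaw.

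**What to change.** Use one definition in the Summary, Section 2 and Section 6:

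1. **Accuracy** is the distance from force-sensing ablation-catheter points, selected by a prespecified recorded-force criterion and not by mTPI, to the mFAM surface as it stood before those points were used to fit or adapt it. Justify the criterion on its own terms; do not cite 5-10 g as the pilot's reference window.
2. **Fit** is the distance to mTPI-acquired points, reported separately under that name.
3. **Sensitivity analysis:** if positions without the new respiratory correction are retained, repeat the accuracy score with them. First confirm that they are available and share a reference frame with the surface.
4. **Earlier cases:** if shown alongside, score them by the same rule.

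The cost is endpoint wording, a data filter, and keeping the surface as it was before adaptation. Section 4.1 already provides for "Automatic import of data recordings (such as position, respiration, and force) from the CARTO® 3 System", and the ablation catheters are already in Section 4.2, so no new equipment is implied. The downsides are fewer scored points, their concentration at ablation sites (so other regions of the atrium go largely unscored), and a probably larger reported distance.
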